8.1.1.3. Deaths and Serious Adverse Events

In the event that a subject has withdrawn consent, no data after the withdrawal of consent date from this subject including death is supposed to appear in the database, which should be part of the data cleaning process. All deaths will be summarized based on the number and percentage of subjects. This summary will classify subjects by primary cause of death. A supportive listing will be generated to provide subject-specific profiles on subjects who died.

All SAEs will be tabulated based on the number and percentage of subjects who experienced the event. Separate summaries will also be provided for study treatment-related SAEs for both GSK3326595 and pembrolizumab where applicable. The frequency and percentage of SAEs will be summarized in descending order of total incidence by PT only.

A study treatment-related SAE is defined as an SAE for which the investigator classifies the relationship to study treatment as "Yes". A worst-case scenario approach will be taken to handle missing data, i.e. the summary table will include events with the relationship to study treatment as 'Yes' or missing.

SAEs are included in the listing of all adverse events. Separate supportive listings with subject-level details will be generated for non-fatal SAEs.

8.1.1.4. Adverse Events Leading to Discontinuation of Study Treatment and Other Significant Adverse Events

The following categories of AEs will be summarized separately in descending order of total incidence by PT only and separate supportive listings will be generated with subject level details for those subjects:

- AEs Leading to Discontinuation of Study Treatment (note: Part 3 subjects will be summarized separately as follows: AEs leading to GSK3326595 discontinuation; AEs leading to pembrolizumab discontinuation. Supportive listings will only be for GSK3326595).
- AEs Leading to Dose Interruptions of GSK3326595.
- AEs Leadings to Dose Reductions of GSK3326595

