5.4. Withdrawal/Stopping Criteria

5.4.1. Discontinuation of Study Treatment

Subjects will receive study treatment until disease progression, death or unacceptable adverse event, including meeting stopping criteria for liver chemistry, hematologic/non-hematologic toxicity, or corrected QT interval duration (QTc) prolongation, as defined in Section 5.4.5 through Section 5.4.7.

In addition, study treatment may be permanently discontinued for any of the following reasons:

- deviation(s) from the protocol
- request of the subject or proxy
- investigator's discretion
- subject is lost to follow-up
- study is closed or terminated.
- study drug is no longer available

Note that discontinuation from study treatment does NOT equal complete withdrawal from the study (all efforts should be made to keep subjects with a diagnosis of ACC who withdraw from treatment on study for survival follow-up).

Subjects in Part 3 may be treated past progression as described in Section 14.4.4.

Subjects in Parts 1 and 2 with equivocal progression or with rising tumor markers in the absence of radiographic progression may continue on study therapy provided that safety related stopping criteria are not met.

Subjects in Parts 1 and 2 with progressive disease (PD) may remain on study on a caseby-case basis (e.g., as long as the Investigator and the GSK Medical Monitor concur that the subject could continue to receive benefit, the subject is not experiencing serious toxicity, and there is no alternative treatment that is likely to benefit the subject). Discussion between the Investigator and the Medical Monitor must occur in order for a subject to continue study treatment once PD has been confirmed. Subjects who continue on study beyond confirmed progression should continue to undergo all assessments described in the Time and Events Table. Subjects who demonstrate continued progression

at subsequent scheduled scans may be required to discontinue therapy at the discretion of the Investigator and the Medical Monitor.

For subjects in all Parts of the study, the primary reason study treatment was permanently discontinued must be documented in the subject's medical records and electronic case report form (eCRF).

If the subject voluntarily discontinues from treatment due to toxicity, 'adverse event' will be recorded as the primary reason for permanent discontinuation on the eCRF.

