5.4.3. Withdrawal from the study

A subject may withdraw from the study at any time at his/her own request or may be withdrawn at any time at the discretion of the investigator for safety, behavioral or administrative reasons, as described above.

If a subject withdraws consent, the investigator/site staff must specifically ask if they are withdrawing consent to:

- Further participation in the study including any further follow-up (eg, survival calls, consultation of medical records for vital status)
- Further participation in study assessments *excluding* survival follow-up [relevant for Part 2 and Part 3 subjects only] (eg, survival calls, consultation of medical records for vital status)
- The use of optional and/or mandatory biological samples that have not already been analysed (remaining unanalyzed samples must be destroyed)

The investigator must document consent withdrawal in the site study records and CRF.

If the subject has actively withdrawn consent to the processing of their personal data, the vital status of the subject can be obtained by site personnel from publicly available resources, where it is possible to do so under applicable local laws.

Following Protocol Amendment 8 implementation, all recruited subjects who no longer receive study treatment will stop entirely and only subjects still deriving benefit from GSK3326595 as assessed by the Investigator may continue to receive study treatment. At the point of discontinuation of study treatment (including 30-day safety follow up), subjects will be considered to have completed the study. If a subject withdraws consent, the investigator/ site staff must document consent withdrawal in the site study records.

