5.4.4. End of Survival Follow-up

In Part 2 or Part 3 (whichever is latest), unless a disease cohort is closed early, survival follow-up will continue in each cohort until approximately 70% of the total number of subjects have progressed or died. At such time, the cohort will be closed and any further follow-up on subjects enrolled in that cohort will cease. Subjects with radiologically confirmed lack of disease progression who are still receiving GSK3326595 at the time of study completion may continue treatment through a separate mechanism (e.g., roll-over protocol).

Note: following Protocol Amendment 7, survival follow-up will only be conducted for subjects in Part 1 and Part 2 with a diagnosis of ACC. Survival follow-up with continue until approximately 70% of ACC subjects have died.

Following Protocol Amendment 8 implementation, all recruited subjects who no longer receive study treatment will stop entirely and only subjects still deriving benefit from GSK3326595 as assessed by the Investigator may continue to receive study treatment.

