7.2.7. Overall Survival (OS)

Overall survival (OS) is defined as the interval of time (in months) between the start date of treatment and the date of death due to any cause. This will be summarized for the Part 2 ACC TN cohort and all ACC subjects across Part 1 and Part 2.

For subjects who are alive, time of death will be censored at the date of last contact. The date of death should be taken from the *Record of Death* eCRF page. Death on study due to any cause will be included. Survival will be summarized using the Kaplan-Meier method. Estimates of 1st quartile survival, median survival, and 3rd quartile survival will be presented with 95% confidence intervals based on the Brookmeyer-Crowley method (Brookmeyer, 1982).

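### SAP 8.1.1.3 bars every death after consent withdrawal without separating the withdrawal types in protocol 5.4.3, so read literally it drops permitted deaths from ACC overall survival and the death summary

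*SAP*

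**What the plan says.** SAP 8.1.1.3, on deaths and serious adverse events, sets one rule for a subject who has withdrawn consent: "no data after the withdrawal of consent date from this subject including death is supposed to appear in the database". It assigns enforcement to data cleaning.

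Protocol 5.4.3 treats withdrawal of consent as several different things, and the site must ask which applies:

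- withdrawal from all participation, including survival calls and checks of medical records;
- withdrawal from assessments but not from "survival follow-up [relevant for Part 2 and Part 3 subjects only] (eg, survival calls, consultation of medical records for vital status";
- withdrawal of consent to use samples not yet analysed.

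Separately, for a subject who has withdrawn consent to the processing of personal data, the protocol says that "the vital status of the subject can be obtained by site personnel from publicly available resources, where it is possible to do so" under local law.

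For OS, SAP 7.2.7 says "Death on study due to any cause will be included". It takes the death date from the Record of Death eCRF page and censors subjects who are alive at last contact. On the population it says "This will be summarized for the Part 2 ACC TN cohort and all ACC subjects across Part 1 and Part 2". It neither refers to SAP 8.1.1.3 nor makes an exception for withdrawn consent. SAP 2.1 declares no deviation from the protocol analysis and does not list the consent rule among its exceptions.

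**The concern.** The SAP rule has one trigger, and the protocol has several situations that could set it off. A data cleaner who applies the sentence as written would delete the death of a subject who stopped scans, agreed to survival calls and later died. The same would happen to a death found in a public register.

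The sentence sits in the safety section but governs the whole database. A death missing from the database cannot be an OS event, nor can it appear in the summary of deaths (SAP Table 3.30). The issue falls mainly on ACC, because after Amendment 7 "survival follow-up will only be conducted for subjects in Part 1 and Part 2 with a diagnosis of ACC". OS is a secondary endpoint for the ACC tablet cohort, and the SAP extends it to all ACC subjects in Parts 1 and 2. If subjects who withdraw have a worse prognosis than those who stay, losing their deaths makes survival look longer than it was.

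**Working it through.** The documents give no figure to reproduce, so the main check is a comparison of the texts.

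**1. The rule against each situation in protocol 5.4.3**

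| Situation | Protocol 5.4.3 | SAP 8.1.1.3 read literally | Conflict |
|---|---|---|---|
| All participation and follow-up withdrawn | No further follow-up | Later data, including death, excluded | None, unless a public record of death exists |
| Assessments only (Parts 2 and 3) | Survival follow-up continues | Death excluded | Yes, and also with SAP 7.2.7 |
| Sample use only | Samples destroyed, nothing else affected | All later data excluded | Yes, though plainly not intended |
| Consent to data processing withdrawn | Vital status may come from public sources, where lawful | Death excluded | Yes: a permitted source is discarded |

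**2. If the rule means full withdrawal only.** The second and third rows drop out. The public-source provision remains, and the SAP still discards a death that the protocol allows to be obtained.

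**3. How many deaths could be involved.** The share of subjects who withdraw from assessments only is not in the documents, so assume 2%, 5% or 10%, with mortality like the rest and withdrawal always before death. Take the planned maximum of 50 tablet subjects and 38 capsule subjects (protocol 11.5), and the 70% mortality at which ACC survival follow-up was due to end (protocol 5.4.4).

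- Tablet cohort: 50 × 0.70 = 35 deaths. Removed: 35 × 0.02 = 0.7, 35 × 0.05 = 1.8, 35 × 0.10 = 3.5.
- Both cohorts: 88 × 0.70 = 61.6 deaths. Removed: 1.2, 3.1, 6.2.

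These are ceilings on cohort size. Recruitment to the tablet cohort was stopped, and Amendment 8 ends collection for subjects off treatment once it is in force at a site. The assessments-only option does not cover Part 1 ACC subjects.

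**4. Effect on median OS.** Let w be the share of deaths lost, and assume a constant hazard, estimated as deaths divided by follow-up time.

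- If withdrawal is unrelated to prognosis, deaths and follow-up time fall in proportion and the expected ratio of medians is 1.00.
- If each lost death is preceded immediately by withdrawal, almost no follow-up time is lost. The ratio is then 1/(1 − w): 1.05, 1.11 and 1.25 for w = 5%, 10% and 20%. This is an upper limit.
- If withdrawal falls at a random point before death, half of those subjects' time is lost as well. Set the hazard to 1. With 70% dead, follow-up per subject is 0.70 and its length is −ln 0.30 = 1.204. Survivors contribute 0.30 × 1.204 = 0.361, so those who die contribute 0.339. Half of that is 0.169, and 0.169/0.70 = 0.242. The ratio is (1 − 0.242w)/(1 − w): 1.04, 1.08 and 1.19 for the same w.

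**The case against.** The best defence is that the sentence means withdrawal from the study altogether. Protocol 5.5 counts a Part 2 or Part 3 subject as having completed by withdrawing consent to any further participation, and it treats survival follow-up as part of the study. On that reading a subject who leaves assessments but accepts survival calls is still on study, and SAP 7.2.7 counts the death. The sample-use option supports this, since nobody would purge clinical data because a subject asked for samples to be destroyed. This is probably what was meant. It shows that the wording needs a limit, but the SAP does not state one.

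Second, the public-source provision is a permission. It does not say that such deaths will be entered or analysed, so leaving them out breaches no protocol requirement. That stands, but the SAP then closes a source that the protocol opens without declaring it.

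A reader might also be tempted by three stronger readings that the documents do not support.

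- *Deaths will certainly be removed.* This depends on how the sentence is applied in data cleaning, which the documents do not show.
- *Median OS is lengthened by 5%, 11% or 25%.* Those values need withdrawal immediately before death, and no withdrawal rate is documented. Nothing in the documents says that withdrawing subjects are sicker.
- *Protocol 5.4.1 contradicts the rule because "all efforts should be made to keep subjects with a diagnosis of ACC who withdraw from treatment on study for survival follow-up".* That passage concerns stopping treatment, whereas the SAP rule is triggered by withdrawal of consent.

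**Conclusion.** The point holds as a defect in a stated rule. Applied literally, SAP 8.1.1.3 removes deaths that protocol 5.4.3 allows to be collected and SAP 7.2.7 says to count. Under the narrowest reading it still discards lawfully obtained public-record deaths.

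The size is unknown and probably small: a few deaths at most under the assumed 2% to 10% range, and only deaths recorded before Amendment 8 ended collection at a site. Bias in OS is upward only if withdrawal is related to prognosis. The 1/(1 − w) figures are upper limits and should not be reported as an expected effect. OS is secondary and descriptive, and the primary response rate is unaffected. The change should be made because it is cheap and the rule, as written, can give a wrong OS estimate and a wrong count of deaths.

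**What to change.** - Reword SAP 8.1.1.3 so that data after withdrawal are excluded only to the extent of the consent withdrawn under protocol 5.4.3.
- Keep deaths and last-known-alive dates for subjects who withdrew from assessments only, and any vital status lawfully obtained from public sources. Use them in OS and in the death summary.
- State in SAP 7.2.7 that subjects who withdrew from all follow-up, with no public record of death, are censored at last contact on or before withdrawal.
- Report the number of subjects in each withdrawal category.
- If cleaning has already been done, check whether any deaths were removed under this rule, restore those that are permitted, and describe the rule in the study report.

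The cost is a few sentences in the SAP and a matching change to the cleaning rule, with no new visits. The protocol requires sites to ask about the type of withdrawal and to document consent withdrawal, but it does not say that the chosen option is recorded in the CRF. The type may therefore have to be retrieved from site records.

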6. STUDY TREATMENT

6.1. GSK3326595 and Pembrolizumab

The term 'study treatment' is used throughout the protocol to describe GSK3326595 (or GSK3326595 plus pembrolizumab for subjects in Part 3) received by the subject as per the protocol design. Post Protocol Amendment 8 implementation, study drug GSK3326595 will be provided until the end of availability of study treatment, which is anticipated to be Q3 2023.

Study Treatment												
Product name:	GSK3326595	GSK3326595 Tablets	Pembrolizumab									
	Capsules											

Study Treatment													
Product name:	GSK3326595	GSK3326595 Tablets	Pembrolizumab										
	Capsules												
Dosage form:	Capsules	Tablet	Solution for infusion										
Unit dose	100 mg as free	100 mg as free base	100 mg/4 mL										
strength(s)/Dosage	base												
level(s):													
Route of	Oral		IV infusion										
Administration													
Dosing	The dosing regimer	n is detailed in Section 8.1	Administer diluted product										
instructions:	and is designed to	permit collection of detailed	once Q3W (refer to SRM										
	safety and PK data	. GSK3326595 is to be	for infusion time)										
	administered orally	with water (approximately											
	200 mL) at approximately the same time of												
	day (± 4 hours) with												
	before and 2 h after	r each dose. If a dose is											
	delayed by more th	an 4 hours, the subject											
	should not take that	t dose and should mark the											
	dose as "not taken"	. On serial PK days and for											
	two days prior (Day	vs 13 through 16), subjects											
	should attempt to ta	ake GSK3326595 within a											
	1 h window (i.e., 23	-25 hours after the last											
	dose). Capsules/ta	iblets should not be chewed											
	or crushed. If dose	regimen requires more											
	than one capsule/ta	ablet per dose, the											
	capsules/tablet sho	uid be taken one at a time.											
Physical	Opaque white	vvnite to almost white film	Concentrate for solution										
description:	capsules (size	coated tablets with no	tor infusion, clear to										
	00)	markings	slightly opalescent,										
			colourless to slightly										
			yellow solution, pH 5.2 –										
NOTE: These formulation	details are current at the	time of protocol finalization and ma	0.0.										
			ay be upualeu in olilei										

documents (e.g., SRM and/or informed consent form) without requiring protocol amendment

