8.1.1.2. Adverse Events

An overview summary of AEs, including counts and percentages of subjects with any AE, AEs related to study treatment, AEs leading to permanent discontinuation of study treatment, AEs leading to dose reductions, AEs leading to dose delays/interruptions, SAEs, SAEs related to study treatment, fatal SAEs, and fatal SAEs related to study treatment will be produced.

The relationship between MedDRA system organ class (SOC), preferred term (PT), and verbatim text will be listed.

Adverse events (AEs) will be graded according to the CTCAE, Version 4.03, [Basch, 2014]. Adverse events will be coded to the preferred term (PT) level using the Medical Dictionary for Regulatory Affairs (MedDRA dictionary).

A summary of number and percentage of subjects with any adverse events by maximum grade will be produced. AEs will be sorted by preferred term in descending order of total incidence. The summary will use the following algorithms for counting the subject:

- **Preferred term row**: Subjects experiencing the same AE preferred term several times with different grades will only be counted once with the maximum grade.
- Any event row: Each subject with at least one adverse event will be counted only once at the maximum grade no matter how many events they have.

In addition, the frequency and percentage of AEs (all grades) will be summarized and displayed in two ways: 1) in descending order of total incidence by PT only and 2) in descending order of total incidence by SOC and PT. In the SOC row, the number of subjects with multiple events under the same system organ class will be counted once.

A separate summary will be provided for study treatment-related AEs. A study treatmentrelated AE is defined as an AE for which the investigator classifies the relationship to study treatment as "Yes". A worst-case scenario approach will be taken to handle missing relatedness data, i.e., the summary table will include events with the relationship to study treatment as 'Yes' or missing. The summary table will be displayed in descending order of total incidence by PT and by maximum grade sorted by PT in descending order of total incidence.

For Part 3 treatment-related AE, the below 3 sets of tables will be generated by system organ class, preferred term, and maximum grade:

- AEs related to GSK3326595
- AEs related or pembrolizumab
- AEs related to GSK3326595 and pembrolizumab

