15.12.7. Safety Tables

		IDSL / Example			
No.	Population	Shell	Title	Programming Notes	Deliverable
Advers	e Events				-
3.1	All Treated	AE13	Adverse Event Overview	Including subjects with any AE, AEs related to GSK3326595, Grade 3/4 AEs, Grade 3/4 AEs related to GSK3326595, AEs leading to dose reductions of GSK3326595, AEs leading to dose interruptions of GSK3326595, AEs leading to permanent discontinuation of GSK3326595, SAEs, SAEs related to GSK3326595, fatal SAEs, and fatal SAEs related to GSK3326595 Part 1 (by dose), Part 2 (by cohort), Part 1/Part 2 300mg/400mg/Total/Overall, Part 3 (by dose)	IA, SAC
3.2	All Treated	AE1	Summary of All Adverse Events by System Organ Class and Preferred Term	ICH E3 Part 1 (by dose), Part 2 (by cohort), Part 1/Part 2 300mg/400mg/Total/Overall, Part 3 (by dose)	SAC
3.3	All Treated	AE5B	Summary of All Adverse Events by System Organ Class and Preferred Term and Maximum Grade	ICH E3 Part 1 (by dose), Part 2 (by cohort), Part 1/Part 2 300mg/400mg/Total/Overall, Part 3 (by dose)	SAC
3.4	All Treated	AE1	Summary of All Adverse Events by Preferred Term	ICH E3 Part 1 (by dose), Part 2 (by cohort), Part 1/Part 2 300mg/400mg/Total/Overall, Part 3 (by dose)	SAC
3.5	All Treated	AE3	Summary of Common (>=10%) Adverse Events by Overall Frequency	ICH E3 Part 1 (by dose), Part 2 (by cohort), Part 1/Part 2 300mg/400mg/Total/Overall, Part 3 (by dose)	SAC
3.6	All Treated	AE3	Summary of Common (>=10%) Grade 2- 5 Adverse Events by Overall Frequency	ICH E3 Part 1 (by dose), Part 2 (by cohort), Part 1/Part 2 300mg/400mg/Total/Overall, Part 3 (by dose)	SAC
3.7	All Treated	AE1	Summary of All GSK3326595-Related Adverse Events by System Organ Class and Preferred Term	ICH E3 Part 1 (by dose), Part 2 (by cohort), Part 1/Part 2 300mg/400mg/Total/Overall, Part 3 (by dose) Please include a footnote describing how these events are selected (i.e. this	SAC

		IDSL / Example			
No.	Population	Shell	Title	Programming Notes	Deliverable
				table includes events for which the investigator selected as related to GSK only)	
3.8	All Treated	AE5B	Summary of All GSK3326595-Related Adverse Events by System Organ Class and Preferred Term and Maximum Grade	ICH E3 Part 1 (by dose), Part 2 (by cohort), Part 1/Part 2 300mg/400mg/Total/Overall, Part 3 (by dose) Please include a footnote describing how these events are selected (i.e. this table includes events for which the investigator selected as related to GSK only)	SAC

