3.20	All Treated	AE16	Summary of Serious Adverse Events by System Organ Class and Preferred Term (Number of Participants and Occurrences)	FDAAA, EudraCT Part 1 (by dose), Part 2 (by cohort), Part 1/Part 2 300mg/400mg/Total/Overall, Part 3 (by dose)	SAC
3.21	All Treated	AE1	Summary of Adverse Events Leading to Permanent Discontinuation of Study Treatment by System Organ Class and Preferred Term	IDSL Part 1 (by dose), Part 2 (by cohort), Part 1/Part 2 300mg/400mg/Total/Overall, Part 3 (by dose)	SAC
3.23	All Treated	AE3	Summary of Serious Adverse Events Related to GSK3326595 by Preferred Term	Part 1 (by dose), Part 2 (by cohort), Part 1/Part 2 300mg/400mg/Total/Overall, Part 3 (by dose) Please include a footnote describing how these events are selected (i.e. this table includes events for which the investigator selected as related to GSK only)	IA, SAC
3.24	All Treated	ESI2A	Summary of Onset and Duration of First Occurrence of Selected Adverse Events	Anemia, neutropenia, thrombocytopenia (platelet count decrease and thrombocytopenia), fatigue, Part 1 (by dose), Part 2 (by cohort), Part 3 (by dose)	SAC
3.25	All Treated	ESI1	Summary of Event Characteristics of Selected Adverse Events	Anemia, neutropenia, thrombocytopenia (platelet count decrease and thrombocytopenia), fatigue, Part 1 (by dose), Part 2 (by cohort), Part 3 (by dose)	IA, SAC
3.30	All Treated	DD1	Summary of Deaths	ICH E3 Part 1 (by dose), Part 2 (by cohort), Part 1/Part 2 300mg/400mg/Total/Overall, Part 3 (by dose) Report time to death from last dose (in days) as in the mock	SAC

No.	Population	IDSL / Example Shell	Title	Programming Notes	Deliverable
Labora	tory Results		•		
3.31	All Treated	LB1	Summary of Chemistry Changes from Baseline	ICH E3 To include grade increase from Baseline Grade Creatinine	SAC
3.32	All Treated	LB15	Summary of Worst-Case Chemistry Results by Maximum Grade Increase Post-Baseline Relative to Baseline	ICH E3 Report only worst-case post-baseline. Don't report by- visit summary rows. For CTCAE graded tests Part 1 (by dose), Part 2 (by cohort), Part 1/Part 2 300mg/400mg/Total/Overall, Part 3 (by dose)	SAC
3.33	All Treated	LB16	Summary of Worst Case Chemistry Results Relative to Normal Range Post- Baseline Relative to Baseline	ICH E3 Report only worst-case post-baseline. Don't report by- visit summary rows. For non-graded tests Part 1 (by dose), Part 2 (by cohort), Part 1/Part 2 300mg/400mg/Total/Overall, Part 3 (by dose)	SAC

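### Part 3 displays omit the pembrolizumab-related SAE summary that SAP 8.1.1.3 promises, and the 'GSK only' selection note needs one clear definition

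*SAP*

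**What the plan says.** **Related SAEs.** SAP 8.1.1.3 commits to this: "Separate summaries will also be provided for study treatment-related SAEs for both GSK3326595 and pembrolizumab where applicable". It counts an event as related when the investigator's answer is yes or missing. In SAP 15.12.7 the only related-SAE table is Table 3.23, "Summary of Serious Adverse Events Related to GSK3326595 by Preferred Term", produced for Parts 1, 2 and 3. Its programming note asks for a footnote to the effect that "this table includes events for which the investigator selected as related to GSK only".

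**Overview.** SAP 8.1.1.2 says that counts of "SAEs related to study treatment, fatal SAEs, and fatal SAEs related to study treatment will be produced"; it words related AEs and AEs leading to permanent discontinuation in terms of study treatment too. Protocol 6.1 uses that term to "describe GSK3326595 (or GSK3326595 plus pembrolizumab for subjects in Part 3"). The note for Table 3.1, which covers Part 3 by dose, lists instead "SAEs, SAEs related to GSK3326595, fatal SAEs, and fatal SAEs related to GSK3326595", and it also names GSK3326595 alone for related AEs and permanent discontinuation.

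**Discontinuation.** SAP 8.1.1.4 says that "Part 3 subjects will be summarized separately as follows: AEs leading to GSK3326595 discontinuation; AEs leading to pembrolizumab discontinuation". The table listed is 3.21, "Summary of Adverse Events Leading to Permanent Discontinuation of Study Treatment by System Organ Class and Preferred Term", with Part 3 shown by dose and no mention of a split by drug.

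**Related AEs of any seriousness.** For Part 3, SAP 8.1.1.2 specifies three sets: related to GSK3326595, to pembrolizumab, and to both. These correspond to Tables 3.8, 3.10 and 3.12. The notes select 'GSK only' for 3.8 (also for 3.7, 3.13, 3.14 and 3.23), 'Pembro only' for 3.10 and both drugs for 3.12.

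**The concern.** The primary objective of Part 3 is the safety and tolerability of the combination, and SAEs are a named part of its primary endpoint. If the outputs are programmed from the display list, the final report will have no table of SAEs related to pembrolizumab. Its overview will also show related SAEs and related deaths for one of the two drugs only. A reader of the Part 3 columns could take the GSK3326595 rows for the full count of treatment-related serious events.

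The selection notes raise a second question. If 'GSK only' is programmed as an exclusive filter, an SAE attributed to both drugs drops out of Table 3.23. Table 3.1 carries no such restriction, so its row for SAEs related to GSK3326595 could show a different count from Table 3.23 in the same report.

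**Working it through.** No formula in the plan applies here. The check sets each commitment in the SAP text against the displays listed for Part 3.

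| Commitment in the text | Display listed for Part 3 | Met? |
|---|---|---|
| 8.1.1.3: related SAEs, GSK3326595 | Table 3.23 | Yes |
| 8.1.1.3: related SAEs, pembrolizumab | None | No |
| 8.1.1.2: four overview items by study treatment (related AEs, permanent discontinuation, related SAEs, related fatal SAEs) | Table 3.1, the same four items by GSK3326595 | No, for all four |
| 8.1.1.2: related AEs in three sets | Tables 3.8, 3.10, 3.12 | Yes |
| 8.1.1.4: discontinuation AEs by drug | Table 3.21, not split; Tables 1.2 and 1.3 give discontinuation reasons by drug | In part |

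**Tables that name pembrolizumab.** SAP 15.12.7 has five: 3.10 and 3.12 (all AEs), 3.56 (exposure), 3.58 (dose reductions) and 3.60 (dose delays). None is an SAE table.

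**Attribution categories.** An event in Part 3 can be attributed to GSK3326595 alone, to pembrolizumab alone, or to both.

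| Summary | 'GSK only' read as exclusive | 'GSK only' read as any GSK3326595-related event |
|---|---|---|
| Related AEs (3.8, 3.10, 3.12) | 3 of 3 | 3 of 3 |
| Related SAEs (3.23) | 1 of 3 | 2 of 3 |

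SAEs attributed to pembrolizumab alone are missing from the related-SAE summary under both readings. The omission therefore does not depend on how the note is read. Only jointly attributed SAEs do.

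**Agreement between Tables 3.1 and 3.23.** For one Part 3 dose group, let *a* be the subjects with at least one SAE attributed to GSK3326595 alone. Let *b* be the subjects whose GSK3326595-related SAEs are all attributed to both drugs. Taken at its label, the Table 3.1 row counts *a* + *b*. The any-event count in Table 3.23 is *a* under the exclusive reading and *a* + *b* under the inclusive one. The difference is therefore *b* or 0. The documents do not give *b*; if it is 0, the tables agree. As a conversion only, one subject is 1/10 = 10.0 percentage points with 10 subjects per dose, or 1/11 = 9.1 with 11.

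**Where the events still appear.** Tables 3.10 and 3.12 count pembrolizumab-related serious events among all AEs, without marking them as serious. Tables 3.19 and 3.20 count all SAEs, without attribution. Listing 10 covers all AEs and Listing 12 covers non-fatal SAEs.

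**The case against.** The strongest reply is that the promise is hedged and the information is available. SAP 8.1.1.3 says 'where applicable', and SAP 5.1.1 says that only some Part 3 AE tables will be shown by drug. Neither removes the commitment. Part 3 is where pembrolizumab applies, and a general remark about some tables does not override a specific statement about related SAEs.

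The rest of the reply limits the point, and most of it stands. A reader might infer any of the following, and the documents do not support them:

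- *Pembrolizumab-related serious events go unreported.* They remain in Tables 3.10, 3.12, 3.19 and 3.20 and in the listings. What is absent is a summary restricted to related SAEs.
- *The 'GSK only' note is a proven error.* The title of Table 3.23 has no such restriction. The same note also serves Parts 1 and 2, where it excludes nothing, so it may be loose wording. It is an ambiguity to settle.
- *Every GSK3326595 row in Table 3.1 is a defect.* SAP 8.1.1.4 itself limits dose reductions and interruptions to GSK3326595, and 8.1.1.2 never promised a related Grade 3/4 row. Only the four study-treatment items conflict with the text.
- *Discontinuation by drug is missing altogether.* Tables 1.2 and 1.3 give reasons by drug; only the preferred-term breakdown is absent.
- *Dose decisions could be affected.* Protocol 4.4.4.1 already counts toxicity attributed to either drug or to the combination.

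The mock shells are not available, and the note for Table 3.1 opens with the word 'Including', so a shell might hold more rows. Nothing in the documents says that it does.

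**Conclusion.** The SAP text and its display list conflict on Part 3, and this should be corrected. One promised related-SAE table is not listed, four overview rows are narrower than the text defines them, and one discontinuation table lacks the promised split by drug. An SAE or death attributed to pembrolizumab alone would appear in no related-SAE summary. This conclusion rests only on the display list being complete as published.

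The 'GSK only' note is a lesser, separate point. Read literally beside the notes on Tables 3.10 and 3.12, it would remove jointly attributed SAEs from Table 3.23. The intention is not stated and the effect cannot be sized.

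The consequence is confined to how Part 3 safety is summarised in the final report. The publication interims described in SAP 3.1.3 and 3.1.9 cover Parts 1 and 2, Part 3 tests no hypothesis, and no data are missing.

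**What to change.** 1. Add a Part 3 table of pembrolizumab-related SAEs by preferred term, as a counterpart to Table 3.23.
2. In Table 3.1 for Part 3, add rows so that related AEs, related SAEs, related fatal SAEs and permanent discontinuation reflect study treatment, as SAP 8.1.1.2 says.
3. For Part 3, define GSK3326595-related once: relationship to GSK3326595 recorded as yes or missing, whatever the answer for pembrolizumab. Apply it to every table with that label (3.1, 3.7, 3.8, 3.13, 3.14 and 3.23). Define pembrolizumab-related in the same way for Table 3.10 and the new table. Keep Table 3.12 for events related to both, and correct the footnotes. Because the first 14 days of Part 3 are GSK3326595 alone, state how a blank pembrolizumab answer is handled for events before the first infusion.
4. Split Table 3.21 by drug for Part 3, as SAP 8.1.1.4 says.

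The cost is one new table, a few rows, a split, and changes to filters and footnotes; no new data are needed. An event may then appear in more than one table, which a footnote can explain.
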